5.7 Poolability Analysis

Patients may be recruited from up to two study sites. In the case that all the patients in this study are recruited from only one site, poolability analysis is not applicable. However, if more than one study site is involved, we may present the results stratified by study sites.

5.8 Safety Analyses

Adverse events (AE) will be reported for the intent-to-treat set. AEs will be tabulated with the number of events and affected patients for each event type and for all types combined. Rates will be reported as the number of patients who experience at least one event during the analysis interval out of the total number of patients with follow-up to the beginning of the analysis interval. Serious adverse events will

Statistical Analysis Plan		Page 17 of 17
Sponsor SunBio Inc.	Study Clinical Evaluation of MucoPEG for Xerostomia	Version 1.1

also be tabulated. The rate of all AEs and SAEs reported in the study will be reported by product and by treatment period.

All AEs and SAEs will also be summarized by relatedness to the products under investigation as described above. Details of such events will also be reported in listing format.

5.9 Subgroup Analyses

Analyses will be stratified by study site. Subgroup analysis of the primary endpoints will be carried out for sex and age group (below the median age of the study sample versus above the median age). These analyses are intended to demonstrate consistency of results across subgroups.

Heterogeneity between subgroups will be examined in a regression model that includes the treatment, subgroup and their interaction. Additional exploratory analysis may be performed to understand any variations in the outcomes between subgroups.

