8.3 Inclusion Criteria

Individuals must meet all of the inclusion criteria and none of the exclusion criteria to be eligible to participate in the study.

The inclusion criteria are:

1. Must have read, understood and signed an informed consent prior to entering the study
2. Must be 18 years of age or older
3. Good general and mental health with, in the opinion of the investigator or their medically qualified designee, no clinically relevant or significant abnormalities found on examination of the oral cavity or in their medical history
4. Participant with a Challacombe Scale score of 1 or higher
5. Participant agrees not to eat, drink, chew tobacco, chew gum, smoke, brush or floss their teeth for 2 hours prior to study visits
6. Participant agrees not to use any oral care products or any type of breath mint or lozenges for 2 hours prior to study visits
7. Participant agrees not to consume any food or liquid during the study visits, except for what is provided by the study research staff (e.g., water, MucoPEG™ and Biotène® Dry Mouth Gentle Oral Rinse during evaluation periods)
8. Participant agrees to using clinical oral care supplies provided by the investigators and no other products during the entire study
9. Understands and is willing and able to comply with all study procedures and restrictions

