3.3 Study Assessments

Patients are considered to be enrolled in this study after placing their signature on the consent form at Visit 1. Their eligibility to proceed and their concomitant medications will then be checked. Before Period 1 (the first use of MucoPEG or Biotène), patients will undergo one week of “washout” period.

During Period 1, which will last for two weeks, patients will use one of the products twice daily and will be assessed on the first day (Visit 2), seventh day (Visit 3) and fourteenth day (Visit 4) using the VAS, DMRQ, DMI, PPAQ, PPUQ. Information from symptom diary, medications, clinical examination and adverse events will also be recorded.

Another washout period of one week follows Period 1. The assessments for the second treatment will have the same pattern, with Visit 5, 6 and 7 to take place within Period 2.

4 Sample Size Determination

The hypotheses for this study are

- Null hypothesis
Change in VAS after MucoPEG minus change in VAS after Biotène ≥ 0
- Alternative hypothesis
Change in VAS after MucoPEG minus change in VAS after Biotène < 0

The change in VAS associated with each product will be calculated as the value of VAS at two hours after the final dose at Visit 4 minus the value of VAS before the first dose at Visit 2 for the first treatment period. Since the Visual Analogue Scale is constructed such that 0 = no symptom and 10 = most severe symptom, an improvement in symptom is represented by a negative change in its measurement. The hypotheses are to test whether patients would experience greater improvement in their symptoms after a course of MucoPEG.

Statistical Analysis Plan		Page 12 of 17
Sponsor SunBio Inc.	Study Clinical Evaluation of MucoPEG for Xerostomia	Version 1.1

The change in VAS for the second treatment period will be calculated in a similar way from the value of VAS before the first dose at Visit 5 and the value of VAS at two hours after the final dose at Visit 7.

Assuming the average difference between randomization groups is -1.25, a common standard deviation of 1.50 and a Type I error of 0.05 (one-sided probability), an effective sample size of 38 patients will provide 80% power to reject the null hypothesis of no difference between the two products (MucoPEG versus Biotène).

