For comparing the proportion of patients giving a response of "Very Good" or "Significant / Excellent" in the Dry Mouth Relief Questionnaire, an effective sample size of 32 patients will provide 80% power to demonstrate a clinical improvement associated with MucoPEG over Biotène. We assumed a difference of 0.20 between the proportions, a standard deviation of 0.45 and a Type I error rate of 0.05.

Since the effective sample size for the analysis of VAS is greater than that of the Dry Mouth Relief Questionnaire, and effective sample size of 38 patients will be used. Assuming a 10% loss to follow-up, total enrolment for this study is approximately 42 patients.

5 Statistical Analyses

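### The age heterogeneity test uses a median split although a regression is already planned; a continuous treatment-by-age interaction would keep more information if the effect changes roughly linearly with age

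*SAP*

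**What the plan says.** SAP 5.9 plans subgroup analyses of the primary endpoints by sex and by age. The age groups are "below the median age of the study sample versus above the median age". The aim is stated: "These analyses are intended to demonstrate consistency of results across subgroups". The method is a regression: "Heterogeneity between subgroups will be examined in a regression model that includes the treatment, subgroup and their interaction". For age, the subgroup term is therefore a two-level factor. No model with age as a continuous variable is specified. There is one open allowance: "Additional exploratory analysis may be performed to understand any variations in the outcomes between subgroups". It names no method and commits to nothing.

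On age itself, Protocol 8.3 says only "Must be 18 years of age or older". Neither document gives an expected mean, standard deviation or shape.

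The trial is sized for the main effect only. SAP section 4 assumes that the difference "is -1.25, a common standard deviation of 1.50 and a Type I error of 0.05 (one-sided probability") and concludes that "an effective sample size of 38 patients will provide 80% power to reject the null hypothesis". Enrolment follows from that: "Assuming a 10% loss to follow-up, total enrolment for this study is approximately 42 patients". No figure is given for the power of any interaction.

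**The concern.** A median split treats everyone on the same side of the cut as having the same age. It ignores the difference between a patient just above the cut and one decades above it. When a regression is already planned, using age as recorded costs nothing extra and usually says more.

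The stated aim makes this matter a little more than usual. The analysis is meant to support a message of consistency, so a non-significant interaction will tend to be read as reassurance. The weaker the test, the more easily it gives that reassurance whether or not the effect varies. In a trial sized for the main effect the interaction test is weak to begin with, and a coarser age variable weakens it further.

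There is also a small gap in the wording: a patient whose age equals the sample median belongs to neither group.

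**Working it through.** **1. The plan's own figure.** Inputs from SAP section 4: difference 1.25 in size, SD 1.50, one-sided 0.05, power 80%. As a two-sample t-test with the noncentral t distribution, 18 per group gives 79.0% power and 19 per group gives 80.9%, so 2 × 19 = 38. Then 38/0.9 = 42.2, stated as approximately 42. The plan's figure is reproduced. It concerns the main effect and says nothing about interactions.

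**2. How weak the interaction test is before any choice about age.** SAP 5.6.1 compares the products within each treatment period, about 19 versus 19. SAP 5.9 does not say whether its regression is per period or within patient; take the per-period layout as an illustration. A median split leaves 19/2 = 9.5 patients per treatment-by-age cell.
- SE of the interaction = 1.50 × √(4/9.5) = 0.97 VAS points.
- For an interaction as large as the whole assumed effect, 1.25/0.97 = 1.28. Power at two-sided 0.05 is about 24% with the t distribution (25% by the normal approximation).
- 80% power needs (1.96 + 0.84) × 0.97 = 2.7 VAS points.

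A within-patient analysis would do better, by an amount the documents do not let one calculate.

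**3. What the median split costs.** Suppose the treatment effect changes linearly with age and age is balanced between the randomised groups. The information on that trend kept by the split, relative to continuous age, is the squared correlation between age and the split indicator. For a cut at the median this correlation is E|age − median| / SD(age).
- Normal age: √(2/π) = 0.798; squared, 2/π = 0.637. Loss 36%.
- Uniform age: (range/4) / (range/√12) = 0.866; squared, 0.75. Loss 25%.
- Other shapes, one million simulated values each: well-separated bimodal 13.5%, Beta(2,2) 30%, left-skewed Beta(5,2) 35%, t with 5 df 46%, lognormal (log-SD 0.5) 48%, exponential 52%.

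The ratio is the same for a per-period or a within-patient regression.

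**4. The same loss in other terms.** With 38 patients, the split carries the trend information of 38 × 0.637 = 24 patients with continuous age (normal), or 38 × 0.75 = 28.5 (uniform). Take a test with 80% power at two-sided 0.05 on continuous age, so a noncentrality of 1.960 + 0.842 = 2.802:
- normal: 2.802 × 0.798 − 1.960 = 0.28, power 61%;
- uniform: 2.802 × 0.866 − 1.960 = 0.47, power 68%.

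**5. The reverse case.** If the effect is flat on each side of the median and jumps there, the two-level factor is the correct model and loses essentially nothing. The squared correlation is symmetric, so the continuous term would then keep only 64% (normal) or 75% (uniform).

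**6. Patients at the median.** Assumption: ages in whole years, normal, mean 55, SD 8 to 15. With N = 38 or 42, a mean of 1.0 to 2.0 patients sit at the median, and in 43% to 63% of simulated samples nobody does. With N = 37 or 41 there is always at least one, with a mean of 2.0 to 3.0. For uniform ages from 18 to 80 the means are 0.68 (N = 42) and 1.65 (N = 41). If age is computed from full dates of birth, ties almost vanish at N = 42 (mean 0.003), and an odd N leaves exactly one patient. Under normal whole-year ages the split keeps about 0.64 of the information with the tied patients included and 0.66 to 0.68 with them left out. The tie gap is therefore not the source of the loss.

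**The case against.** The best defence is that this is a supportive analysis. No primary result, analysis set or success criterion depends on it. A median split gives two groups of similar size in a small trial and is easy to display, and the allowance for exploratory work could include continuous age. All of that stands, and it limits the importance of the point. The allowance, however, commits to nothing.

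A second defence is that the size of the loss is assumed. That also stands. A reader might infer that about a third of the information is lost as a matter of fact. The documents do not support that: they give no age distribution and no reason to expect a linear trend.

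A reader might also infer that the loss arises because patients at the median are left out. Step 6 shows otherwise. Few patients are affected, often none when N is even, and any analyst would assign them sensibly.

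One might further object that a sample median is not a fixed age and so cannot be carried to another study. That is a preference. SAP 5.9 looks for consistency within this trial, and the fix below keeps the median for display.

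Finally, timing. The SAP's version history says the misstated primary hypotheses were found after database lock, and that the sponsor had examined results for the secondary VAS changes. Altering a model at that stage can look data-driven. This is a reason to disclose the change, not a reason against it. Conversely, the documents do not suggest that the age split itself was chosen on seeing data: neither change listed for version 1.1 concerns SAP 5.9.

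**Conclusion.** The point holds as a cheap improvement of low importance. For the stated purpose, a continuous treatment-by-age interaction is the better default, because it uses the age data in a regression that is already planned.

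The gain is conditional. For a roughly linear change of effect with age, the split loses 36% (normal age) or 25% (uniform age), with 13.5% to 52% across the shapes tried. For a step at the median it loses essentially nothing. Age distribution and trend shape are both assumptions.

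Continuous age would not turn this into a strong test. On the per-period illustration, even an interaction as large as the assumed treatment effect has about 24% power with the split. A non-significant result should not be reported as evidence of consistency under either method; the confidence interval is what shows how much variation remains possible. The primary result is unaffected.

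**What to change.** In SAP 5.9:
- In the heterogeneity model, enter age as a continuous variable in the treatment-by-age interaction. Report the interaction with its confidence interval: VAS points per 10 years for change in VAS, and a stated scale for the DMRQ response, such as log-odds or risk difference per 10 years.
- Keep the median split for display only, worded *at or below the median* versus *above the median*. This closes the tie gap but recovers no information.
- Record the change as made after database lock and as supportive, with its rationale, by the route in SAP section 6.

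The cost is a short edit to SAP 5.9 and the documentation of a post-lock change. Protocol 9.2 asks only for demographics without listing items. SAP 5.3 covers the case where only the year of birth is known by placing the birthday at mid-year, an error of about six months at most, which is negligible for a slope per 10 years. The statistical downside is that the slope assumes a linear trend; the retained median-split display gives a rough view of a step-like pattern.

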5.10 Interim Analyses

No interim analyses are planned.

5.11 Protocol Deviations

Deviations from the procedures outlined in the protocol will be reported on the CRF. Protocol deviations will be summarized for all deviations and by type with event counts and number of subjects with at least one deviation.

6 Changes from Planned Analyses

Any changes to planned statistical analyses determined necessary prior to performing the analyses will be documented in an amended Statistical Analysis Plan and approved prior to the analysis when possible. Any other deviations or changes from the planned analyses deemed necessary due to violation of critical underlying statistical assumptions, data characteristics, or missing data will be clearly described in the clinical study report with justification and rationale.

7 Subject Listings

Subject listings will be provided for protocol deviations and for patients experiencing any side effects or adverse events.
